5.7. Equipment

The wound area is measured by an electronic Clinical Outcome Assessment (eCOA) solution delivered by Medidata Solutions Inc. that enables the PI or delegate to take a photo of the wound at every scheduled site visit. The photos are uploaded, stored, and analysed within an Imaging system delivered by Medidata Solution Inc. (Please refer to section 11 Data Management).

5.8. Randomization Procedure

All included subjects that meet the inclusion and exclusion criteria will be randomized to one of two treatment groups. Randomization will be centralized using Medidata RAVE and stratified based on wound type (VLU or DFU).

5.9. Blinding

No blinding will be used in this investigation, as it is not possible to blind the products due to visible differences. The trial statistician will be blinded until database lock to ensure decisions related to data before database lock do not affect the final results.

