5.5. Rationale for selection and measurement of endpoints

The endpoint "Percentage wound area reduction during the investigational test period of four weeks has been selected as the primary endpoint in this investigation. Previous investigations have shown that percentage area reduction is an important indicator for differentiating between healing and non-healing wounds in the first weeks of treatment (6, 7), and for this reason, this has been selected as a primary end point, as an indicator of total wound healing.

To evaluate clinical performance in terms of wound area reduction as an indication of total wound healing, manual wound area measurements with a ruler would be the preferred option, as it is simple and easily available to all practitioners (8),(9). However, there is a risk of overestimating wound area with up to 40%, when using this method (9). For this reason, a planimetric software will be used where the wound is photographed with a ruler or a marker of known dimensions placed at the skin near the wound edge and the image is transferred to a computer and opened in the planimetric software. The ruler or marker is used for calibration of linear dimensions at the image. Once the wound border is manually traced with a computer mouse the area of wound is calculated and displayed.

The picture of the wound will be performed and uploaded by PI or delegated site personnel. The wound dimensions will be manually traced and calculated using a digital photo-planimetry software system.

The secondary endpoint is an objective measurement to evaluate the cost-effectiveness of the investigational product to determine if Biatain® Silicone can replace two dressings (a filler and secondary dressing) as a cost-effective alternative. Cost-effectiveness will be evaluated by the difference in total treatment costs between the two treatments over the period of the study, based on the number of products used during the investigational period and the unit price of the dressing at the time of investigation.

The exploratory endpoints are objective parameters related to the clinical performance to support the primary endpoint, as well as subjective parameters related to subject self-assessment of their quality of life, which is an important patient health outcome measure.

Adverse events and device deficiencies will be collected to ensure safety of the intervention.

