6.6. Subject Identification and Confidentiality

Subjects will be identified in the electronic CRF (eCRF) and any other document transmitted to the sponsor by the principal investigator or clinical site staff, by a unique identification number (subject number).

Data entered into the eCRF are confidential and will only be available to the sponsor (including sponsor delegates), members of data management teams, the statistician and if requested to regulatory authorities.

The Principal Investigator at each clinical investigational site will maintain, as part of the investigator site file, a list identifying all subjects entered in the clinical investigation (Subject Identification Code and Enrolment List). This list is confidential to all others than the Principal Investigator, or designee at the site.

7. Procedures

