- Photo of wound and upload to a digital photo-planimetry software system
- For patients treated with Biatain® Silicone: photo of the dressing next to the wound bed must also be taken to assess conformability with wound bed and uploaded to a digital photo-planimetry software system
- Wound depth (mm)
- Wound assessment based on the Coloplast Wound Assessment Form (Appendix 7)
- Status of wound
- Wound healed (yes/no) if yes, the following assessments do not require completion: cleansing
 of wound, debridement, wound depth, wound assessment based on the Coloplast Wound Assessment Form, dressing application according to randomization, additional relevant wound
 care products and changes in wound dressing
- Dressing application according to randomization and recording of dressing size
- Additional relevant wound care products (e.g., barrier cream)
- Record any changes in wound dressing and specify reason and product(s)
- Record any changes in concomitant medication
- Review potential AE/ADE/SAE/SADE/device deficiencies/Protocol Deviations
- Scheduling next Study visit in the following week.
- Visit 3 must be 14 days after Visit 1 (-2 days)
- Complete eCRF

Site visit (V3), Week 2:

- Number of dressing changes since last scheduled visit and device accountability
- Cleansing of wound according to standard of care
- Debridement (yes/no)
- Conformability assessment on a 5-point Liker scale
- Photo of wound and upload in a digital photo-planimetry software system
- For patients treated with Biatain® Silicone: photo of the dressing next to the wound bed must also be taken to assess conformability with wound bed and uploaded to a digital photo-planimetry software system
- Wound depth (mm)
- Wound assessment based on the Coloplast Wound Assessment Form (Appendix 7)
- Status of wound
- Wound healed (yes/no) if yes, the following assessments do not require completion: cleansing
 of wound, debridement, wound depth, wound assessment based on the Coloplast Wound Assessment Form, dressing application according to randomization, additional relevant wound
 care products and changes in wound dressing
- Dressing application according to randomization and recording of dressing size
- Additional relevant wound care products (e.g., barrier cream)

- Record any changes in wound dressing and specify reason and product(s)
- Record any changes in concomitant medication
- Review potential AE/ADE/SAE/SADE/device deficiencies/Protocol Deviations

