11.1. Data collection and data management

Data management and the final statistical analyses of all measurements described in this protocol are carried out by the Medical Affairs, Coloplast A/S.

Data will be collected through an electronic data capturing (EDC) system on electronic Case Report Forms (eCRF), a secure, internet-based case report form.

The data management system used in this investigation is Rave delivered by Medidata Solutions Inc. The system is designed to be compliant with the FDA requirements of 21 CFR part 11. It is a validated data management system allowing only qualified and trained personnel to enter the system. The system has full audit trail and electronic signature. The system has restricted role-based access control.

Rave EDC, current version 2022.1.1 will be used to collect all study data.

The applications Medidata eCOA and Rave Imaging will be used to collect and measure photos of the wounds. This App is used during the investigation at every site visit where the investigator or

delegated will take a photo of the wound. A trained person will afterwards be drawing the circumference of the wounds and Rave Imaging will calculate the area of the wound. If needed, the investigator will receive an iPhone with the Medidata eCOA solution installed.

The Quality-of-Life questionnaires will be handed out to the subjects and completed on paper.

This system will be used to record all subject information collected in the investigation. for secure data tracking and centralised data monitoring ("remote monitoring") done by monitors, as defined in the monitoring plan.

The principal investigator or designee must be trained in the system prior to getting access. The training is web-based and must be completed before access to the investigation is granted. Only the principal investigator, or delegate, will be authorised to enter data in the eCRF. The sponsor will be responsible for the study specific training the investigator, or designee, in completion of the eCRF.

Principal Investigator, or designee, at the clinical site will perform primary data collection directly into the eCRF or drawn from source-document (medical records) reviews. The eCRF will be completed on a continuous basis starting from the point of enrolling the subject to final follow up.

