Appendix 9: Endpoints and assessments

	Endpoints and assess- ments	Assessed by	V1 (Base- line)	V2	V3	V4	V5 (Termina- tion)
Primary end- point	Percentage wound area reduction during the investigational test period of four weeks	Investiga- tor/ delegate		x	X	x	X
Secondary endpoint	Total treatment costs during the investigational test period based on the number of dressing used during the investigation and the unit price of the products	Investiga- tor/ delegate	x	x	x	x	x
Exploratory endpoints	Percentage wound depth reduction during the investigational test period	Investiga- tor/ delegate	x	х	x	x	x
	Wound bed, wound edge and peri wound skin condition based on visual assessment based on the Coloplast Wound Assessment Form	Investiga- tor/ delegate	x	x	x	x	х
	Conformability of the dressing based on PI or delegates evaluation according to a 5-point Liker scale	Investiga- tor/ delegate			x		x
	Responder defined as a subject reaching ≥ 30% wound area reduction within the 4-week investigational test period (yes/no)	Data Manage- ment					x
	Wound healed during the investigation pe- riod (yes/no)	Investiga- tor/ delegate		x	x	x	x
	Quality of Life evalu- ated by EQ-5D-5L	Subject	х				x
Safety Assessments	Averse events Device Deficiencies	Investiga- tor/ delegate	x	x	х	x	х

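### The reason given for no blinding (the dressings look different) does not apply to the later hand-tracing of stored wound photos, and no section masks the tracer to treatment arm

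*Combined protocol and SAP*

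**What the plan says.** Section 5.9 gives a single reason for the open-label conduct: "No blinding will be used in this investigation, as it is not possible to blind the products due to visible differences". Its next sentence keeps the trial statistician blinded until database lock. No other role is mentioned.

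The area measurement is described elsewhere as a separate, later step:

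- Section 5.5: "The wound dimensions will be manually traced and calculated using a digital photo-planimetry software system".
- Section 5.7: "The photos are uploaded, stored, and analysed within an Imaging system delivered by Medidata Solution Inc".
- Section 11.1, on the investigator or a deputy and the person who follows: "delegated will take a photo of the wound. A trained person will afterwards be drawing the circumference of the wounds". The software then computes the area.

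Section 7.2 adds an image in one arm only, at Visits 2 to 5: "For patients treated with Biatain® Silicone: photo of the dressing next to the wound bed must also be taken to assess conformability". It is uploaded to a digital photo-planimetry system, as the wound photo is.

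Appendix 9 gives investigator/delegate as assessor for the row "Percentage wound area reduction during the investigational test period of four weeks". On access, section 11.1 says "The system has restricted role-based access control", and section 6.6 says "Data entered into the eCRF are confidential and will only be available to the sponsor", followed by further roles. Section 9.3 also lists who may see the eCRF records. None of these texts refers to treatment arm. Section 11.2 points to data management SOPs that are not part of the documents.

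**The concern.** Where a wound border lies on a photograph is a judgement, and here that judgement produces the primary outcome of an open-label trial. The reason in section 5.9 holds for applying the dressing and for bedside assessment. It does not hold for someone who later outlines a wound on a stored image. Read as written, the plan leaves that person unmasked without having considered the step.

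The Biatain-only dressing photos begin at Visit 2, and section 7.2 lists the baseline photo before randomisation. If the tracer can open the dressing photos, a clue to the arm exists at follow-up and not at baseline. Error that arises only at follow-up does not cancel in a percentage change.

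Section 10.4 makes comparable wound area part of the success criterion and sets no numeric margin, so a shift in the estimated difference bears directly on the conclusion. The responder endpoint (at least 30% reduction) uses the same traced areas.

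**Working it through.** **1. Which steps does the stated reason cover?**

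| Step | Does product appearance prevent masking? | Masking stated? |
|---|---|---|
| Applying the dressing | Yes | No (5.9) |
| Wound assessment at site | In practice, yes | No (5.9) |
| Tracing the stored wound photo | No | Not addressed (5.5, 5.7, 11.1) |
| Statistical decisions before lock | No | Yes (5.9) |

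The wound photo and the dressing photo are separate items in sections 7.2 and 7.3, so wound-only images already exist.

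**2. Precision implied by section 10.2.** Inputs: SD 43 points, 40 completers per arm, two-sided 5%.

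- SE of the difference = 43 × √(2/40) = 9.62 points.
- Expected 95% half-width = t(0.975, 78 df) × SE = 1.991 × 9.62 = 19.1 points, inside the plan's 21-point target.
- The probability that the half-width is below 21 comes out at 89.4%, where section 10.2 states 80%. For the single-arm target of 15 points it is 80.6%, where 89% is stated. The two probabilities look interchanged. That is a separate matter and does not affect this point.

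**3. Effect of a one-arm tracing error (hypothetical).** Assume every week-4 area in one arm is mistraced by the same proportion e, with no error at baseline or in the other arm. Since WAR = 100 × (1 − A4/A0), mean WAR in that arm shifts by e × (100 − mean WAR). Neither e nor the mean WAR is given in the documents; both are assumed over a range. Coverage is from the noncentral t with 78 df and noncentrality shift/SE.

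| e | Mean WAR | Shift (points) | Share of half-width | Coverage of 95% CI |
|---|---|---|---|---|
| 5% | 30% | 3.5 | 18% | 93.5% |
| 5% | 40% | 3.0 | 16% | 93.9% |
| 5% | 60% | 2.0 | 10% | 94.5% |
| 10% | 30% | 7.0 | 37% | 88.9% |
| 10% | 40% | 6.0 | 31% | 90.5% |
| 10% | 60% | 4.0 | 21% | 93.0% |

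A normal WAR with SD 43 puts 5.2%, 8.1% and 17.6% of subjects above 100% reduction at means of 30, 40 and 60, so coverage was also simulated with a lognormal area ratio of the same mean and SD (200,000 trials, pooled t, no covariates). At means of 30, 40 and 60, coverage is 95.3, 95.3 and 95.6% with no error; 88.3, 90.0 and 93.2% with 10% under-tracing; and 89.6, 91.1 and 93.6% with 10% over-tracing.

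**4. Responder endpoint.** With 10% under-tracing, an observed reduction of 30% needs a true reduction of only 1 − 0.7/0.9 = 22.2%. Responder rates in the affected arm:

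| Mean WAR | Lognormal ratio | Normal WAR |
|---|---|---|
| 30% | 61.1 → 68.1% (+6.9) | 50.0 → 57.2% (+7.2) |
| 40% | 71.3 → 76.6% (+5.3) | 59.2 → 66.0% (+6.8) |
| 60% | 85.9 → 88.4% (+2.5) | 75.7 → 81.0% (+5.3) |

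With 5% under-tracing the gains are 3.4, 2.7 and 1.3 points (lognormal) or 3.4, 3.3 and 2.6 (normal).

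**5. What does no harm.** The same proportional error at both visits gives A4(1+e)/(A0(1+e)) = A4/A0, a shift of zero. Equal error in both arms largely cancels in the difference.

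**The case against.** The plan is silent on the tracer; that does not show that the tracer knows the arm. Section 11.1 words the tracer as someone other than the photographer, the software computes the area, and access is role-based, so a reader without eCRF rights might never see the allocation. Permissions may be set in the SOPs. The CIP does not spell out arm-level access even for the statistician, whom it does blind, so silence in the access texts is weak evidence. Appendix 9 is weak evidence too: it gives the same assessor for total cost, whose unit prices come from the tariff. The error sizes are invented, and at 5% the loss of coverage is negligible. Masked tracing would leave photo-taking, debridement and the healed judgement with unblinded staff.

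Most of this stands as a limit on what can be claimed: bias is possible, not shown, and Appendix 9 does not settle who traces. It does not remove the point. Section 5.9 is worded as a general rule with one exception, and the tracer is not in that exception. Access limits that do not mention arm are not masking, and a commitment about the primary measurement belongs in the CIP. A partial remedy at the step that generates the primary data is still worth having.

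One objection qualifies the cost. If the tracer is a site delegate who also applies the dressing, that person cannot be masked for that subject, and another trained person would have to trace those photos.

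**Conclusion.** The concern holds. The stated reason for not blinding does not reach the hand-tracing of stored photos, and nothing in the documents masks that step. The size and direction of any bias are unknown. The figures above illustrate one pattern: a constant proportional error confined to week 4 in one arm. Under it, 10% error costs 4 to 7 points on the WAR difference and about 2.5 to 7 points on the responder rate, while 5% error matters little for coverage. They rest on the plan's SD of 43 with 40 completers per arm, and on assumed mean WAR of 30 to 60%. The change should be made, because the risk sits in the primary endpoint and can be reduced at little cost. Confidence is medium, since the unseen SOPs may already provide for masking; if so, the CIP needs only to say it.

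**What to change.** - In sections 5.9 and 11.1, state that the trained person who traces the wound photos is masked to treatment arm, works from coded wound-only images, and has no access to the allocation or to the Biatain dressing photos. The role-based access control already described in section 11.1 can enforce this.
- Limit the no-blinding statement in section 5.9 to product application and site assessments.
- Align the assessor shown for the primary endpoint in Appendix 9 with section 11.1.

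The cost is wording and some set-up of image permissions. Staff who know a subject's allocation may not trace that subject's photos, which matters only if site staff do the tracing. Sample size, visits and the photos taken are unchanged.

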5.10. Total expected duration of the clinical investigation

The dates below are approximate, and no subjects will be enrolled before all required approvals have been obtained. If changes are required, applicable EC and regulatory authorities will be notified. The end of the investigation is defined as the date of the last visit of the last subject.

First subject enrolled: January 2023

Last subject enrolled: January 2024

Last subject completed: February 2024

Final Report: August 2024

6. Clinical Investigation population

According to the sample size calculation (see section 10.2), 80 subjects are required to complete the study. Assuming a drop-out rate of 20%, the required total number of subjects to be enrolled shall be 100. The subjects will be enrolled at >12 sites.

6.1. Eligibility criteria

To be included in the investigation, the subjects must comply with the selection criteria described below.

6.1.1. Inclusion criteria

Table 2: Inclusion criteria

clus	ion criteria	Justification			
1.	Has given written consent to participate by signing the Informed Consent Signature Form	To meet Helsinki declaration			
2.	Is at least 18 years of age and has full legal capacity	To meet Helsinki declaration			
3.	Has a venous leg ulcer (VLU) (C6 of the CEAP classification(1)) or a non-infected diabetic foot ulcer (DFU) with a duration longer than 8 weeks but no longer than 24 months (Appendix 4)	VLUs and DFUs are some of the most prevalent chronic wounds, they are both categorized as hard to heal ulcers and are most likely to require filler and secondary dressing due to exudate levels and dimensions of the wounds. To ensure reasonable recruitment time, both wound types will therefore be included in the study, and stratification will be made to ensure equal distribution of both wound types in the two arms			
4.	Has a wound with depth ¹ down to 20 mm	To comply with product specification of Biatain ® Silicone in terms of conformability			
5.	Has a maximum wound depth ¹ relative to wound diameter ² with specifications presented in table 1	To quantify conformability, it is essential to ensure that the dressing can conform relative to the width of the wound, which means how the foam increases in height (the swelling rise), when exposed to wound fluids, relative to the diameter of the wound. In Coloplast, the definition of a wound bed conforming dressing is defined as a dressing that conforms to an Alpha (α) value of 0.2, which is also the lower specification limit for Biatain® Silicone (18). However swelling rise has demonstrated to reach maximum of ~ 2 cm in tests with fence sizes (simulated wound diameter) ≥ 6 cm (19). Thus, wound-α is therefore not relevant for these wounds in this study due to inclusion criteria #4.			
6.	Has a wound with exudate levels requiring a filler and a standard secondary dressing	To include wounds that would normally require the comparator dressing regime and ensure that the treatment is aligned with the indications of the dressings			

7.	Has acceptance of compression therapy in case of a VLU or off-loading in case of a DFU, according to local standards	To ensure optimal conditions for wound healing, compression therapy must be performed for VLUs, according to standard of care. For DFUs, off-loading must be performed according to standard of care based on subject need (wound location), preference and resources available
8.	For subjects with diabetes, has HbA1c ≤ 10% or ≤ 86 mmol/mol, measured within the last 3 months prior to inclusion	To mitigate the risk of reduced healing due to poorly managed diabetes

Table 1: Specifications related to Inclusion criteria 5

Wound diameter (cm)	Maximum wound depth (mm)			
6.0-10	20			
5.5-5.9	11			
5.0-5.4	10			
4.5-4.9	9			
4.0-4.4	8			
3.5-3.9	7			
3.0-3.4	6			
2.5.2.9	5			
2.0-2.4	4			
1.5-1.9	3			
1.0-1.4	2			

¹ depth at the deepest point in the wound bed ² diameter measured at the widest point of the wound

6.1.2. Exclusion criteria

Table 3: Exclusion criteria

clus	sion criteria	Justification
1.	Wound is infected. For DFUs, has infection severity mild-severe according to the IWGDF/IDSA guideline (Appendix 5). For VLUs, has 2 or more clinical signs of infection as defined in protocol, based on clinical judgement by investigator/tissue viability nurse (Appendix 6)	Anti-microbial dressings are usually used for infected wounds in this study setting, according to recommendation. For identification of infection in DFUs, the validated IWGDF/IDSA system will be used. No similar validated scoring system currently exist for VLUs. For this reason, clinical signs are used as an indicator of infection according to clinical practice; The presence of 2 or more clinical signs of infection, will exclude subjects with VLUs from participating in the study.
2.	Wounds is with exposed tendons, is with bones or has fistulas	Complicated wounds which may require different treatments and have different healing patterns
3.	Wound is with cavity, or is undermined or tunnelling	Due to potential depth of wounds
4.	Subject is receiving chemotherapy	The skin undergoes major changes because o radio- and/or chemotherapy, and therefore it can be more fragile during wound management.
5.	Subject has ankle-brachial pressure index (ABPI) below 0.8 (measured at a frequency according to local standards)	Compression therapy is contraindicated in subjects with low ABPI
6.	Wound is larger than 10 x10 cm	Larger wounds are likely to have a higher %- area reduction which may cause bias in the overall sample size.
7.	Currently enrolled in another wound care device investigation unless co-enrolment has been agreed with the sponsor	To avoid bias

